### **16.9 Inclusion of Women and Minorities**

This study will be available to all eligible patients regardless of race, gender, or ethnic group.

There is no information currently available regarding differential agent effects of this regimen in subsets defined by race, gender, or ethnicity, and there is no reason to expect such differences to exist. Therefore, although the planned analyses will, as always, look for differences in treatment effect based on racial and gender groupings, the sample size is not increased in order to provide additional power for such subset analyses. A total of 120 patients may be enrolled.

Based on prior studies involving similar disease sites, we expect about 6.7% of patients will be classified as minorities by race and about 50% of patients to be women. Expected sizes of racial by gender subsets are shown in the following table:

Racial Categories	DOMESTIC PLANNED ENROLLMENT REPORT					
	Ethnic Categories				Total	
	Not Hispanic or Latino		Hispanic or Latino			
	Female	Male	Female	Male		
American Indian/Alaska Native	1	1	0	0	2	
Asian	4	3	0	0	7	
Native Hawaiian or Other Pacific Islander	0	0	0	0	0	
Black or African American	20	18	0	0	38	
White	157	114	8	4	283	
More Than One Race	0	0	0	0	0	
Total	182	136	8	4	330	

**Ethnic Categories:** **Hispanic or Latino** – a person of Cuban, Mexican, Puerto Rican, South or Central American, or other Spanish culture or origin, regardless of race. The term “Spanish origin” can also be used in addition to “Hispanic or Latino.”

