## 16.0 STATISTICAL CONSIDERATIONS AND METHODOLOGY

### 16.1 Study Design

This is a three-arm randomized clinical trial. The primary goal of this study is to compare the response rate of patients randomized to one of two doses of armodafinil or placebo in terms of a clinically meaningful improvement in patient-reported fatigue of at least a two-point improvement in the 0-10 point Brief Fatigue Inventory usual fatigue item at eight weeks post-treatment initiation. Endpoints will be assessed per arm and compared across arms by comparing each armodafinil arm versus the placebo arm in turn. We make no adjustment for multiple comparisons as we want to err on the side of moving forward the appropriate dose into phase III testing upon the basis of promising information in the proposed trial.

The three arm randomized trial will accrue a maximum of 330 patients to randomize a 100 evaluable patients per arm based on a binary endpoint to armodafinil or placebo.

Bayesian adaptive “shadow” design: Bayes clinical trial designs are becomingly increasingly more popular as alternatives to classic Fisherian designs, especially in the phase I context (110). They have not, however, been applied to cancer control cooperative group clinical trials. As a feasibility exercise, we will use the results of this trial to “shadow” what would have happened if the Bayes design would have been used. This will provide us insights into the relative utility of the Bayes design within the context of cooperative group cancer control clinical trials. The potential advantage of the Bayes approach is that the study likelihood of efficacy is constantly monitored allowing for the possibility of early study completion and therefore a smaller number of patients put at risk (see MD Anderson Cancer Center Technical Report UTMDABTR-002-06 (98). There are a number of logistical and statistical issues that were raised in the review of the concept (which initially proposed a Bayes design) that we decided it would be more prudent to use a classic Fisherian design to run the trial and use a shadow design to obtain preliminary data for planning future cancer control clinical trials using a Bayes approach. The details for the Bayes design are attached as Appendix X.

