### 16.2 Sample Size

On average, we recruit six patients per month for GBM treatment trials. For symptom control studies with heterogeneous populations, such as N05C7 (Concerta), we were able to average 25 patients a month. We have found that symptom management trials targeting symptoms with a high prevalence have rapid accrual. Therefore, for this study, a reasonable conservative estimate for this more homogeneous population would be 8 patients a month. With 330 patients, accrual would be completed in 41 months.

The randomized design to be utilized is described below. Based on our previous work, we estimate that the response rate for the placebo arm will be 10%. We design the study with 100 patients per arm so that the Fisher’s exact test will have 80% power to detect a response rate of 25% with a two-tailed alternative and a 5% Type I error rate for each treatment comparison to the placebo. Again, we are not using a conservative multiple contrasts approach because we want to err on the side of accepting a modest armodafinil effect. We plan to accrue an additional 30 patients to account for patient cancellations, ineligibility, or major treatment violations. Therefore, there will be a maximum of 330 patients accrued to this study unless undue adverse events are encountered.

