## 16.5 Statistical Design

The primary endpoint for the trial is the response rate in terms of a clinically meaningful improvement in patient-reported fatigue, defined as at least a two-point improvement in fatigue as measured by the usual fatigue item from the Brief Fatigue Inventory at 8 weeks. This change

will be from baseline to 8 weeks (after randomization). The design proposed for this study will randomize a maximum of 330 evaluable patients to one of three treatment arms.

**Efficacy stopping rules:** This study will be monitored by Alliance Data and Safety Monitoring Board (DSMB) every 6 months for safety and efficacy. If at any time prior to full accrual the p-value for the Fisher's exact test that an arm is superior to the other arm given all available data falls below 0.001 then consideration will be given to stopping the trial early.

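### Section 16.9 gives 120 patients where its own table and 16.1, 16.2 and 16.5 give 330; 16.5 miscalls the 330 evaluable, the percentages in 16.9 do not fit its table, and Fisher power at 100 per arm is 76%, not 80%

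*Combined protocol and SAP*

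**What the plan says.** The combined protocol and SAP gives the size of the trial in several places.

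- Section 16.1: the trial "will accrue a maximum of 330 patients to randomize a 100 evaluable patients per arm".
- Section 16.2: 100 patients per arm, plus 30 for cancellations, ineligibility and major violations, so that "there will be a maximum of 330 patients accrued to this study unless undue adverse events are encountered".
- Section 16.5: the design "will randomize a maximum of 330 evaluable patients to one of three treatment arms".
- Section 16.9, text: "A total of 120 patients may be enrolled".
- Section 16.9, table: planned enrolment totals 330.
- Appendix X (Bayes shadow design): at most 120 evaluable patients.

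Section 16.9 also says "we expect about 6.7% of patients will be classified as minorities by race", and that about half will be women.

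On power, 16.2 assumes a 10% placebo response rate and claims, for Fisher's exact test with 100 per arm, "80% power to detect a response rate of 25% with a two-tailed alternative and a 5% Type I error rate" for each dose against placebo. Section 16.3 confirms Fisher's exact test as the primary test, and 16.1 makes no multiplicity adjustment.

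**The concern.** The number of patients is the figure on which power, accrual time and monitoring all rest. Section 16.9 puts 120 and 330 a few lines apart and does not say which governs. Section 16.5 uses the right number with the wrong label: if 330 were the evaluable count, the 30 extra patients in 16.2 would have no purpose. The two expected percentages in 16.9 fail against the table they introduce, so correcting the 120 alone would leave that section contradicting itself.

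The power claim depends on the evaluable count, so it has to be checked at each size. Section 16.7 provides for review of accrual at least twice a year and for DSMB reports every six months. Those reviews need one unambiguous ceiling and a power figure that belongs to the size kept.

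**Working it through.** **Inputs.** Placebo 10%, armodafinil 25%, two-sided 5% per comparison, 100 per arm, loss allowance 30 of 330 (all 16.2); Fisher's exact test (16.2, 16.3). Equal allocation is assumed; it is implied by the same 100 in each arm.

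**1. Reproducing the stated 80%.** The pooled-variance normal formula without continuity correction is

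power = Φ[(d − 1.96·SE0) / SE1],

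with d = 0.25 − 0.10 = 0.15, mean rate 0.175, SE0 = √(2 × 0.175 × 0.825 / n) and SE1 = √((0.09 + 0.1875) / n).

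At n = 100: SE0 = 0.0537 and SE1 = 0.0527, so (0.15 − 0.1053)/0.0527 = 0.848 and power = **80.2%**. This matches the stated figure, and the same formula returns n = 100 per arm.

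**2. Power of the named test.** For Fisher's exact test, sum Bin(i; n, 0.10) × Bin(j; n, 0.25) over all pairs (i, j) whose two-sided Fisher p-value is at most 0.05.

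| Per arm | Corresponds to | Fisher exact | Normal formula |
|---|---|---|---|
| 100 | 300 evaluable (16.1, 16.2) | 76.2% | 80.2% |
| 110 | 330 evaluable (16.5 as worded) | 80.4% | 83.8% |
| 40 | 120, no losses (16.9 sentence) | 33.4% | 42.1% |
| 36 | 120 with the plan's loss rate | 28.7% | 38.6% |

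Last row: 120 × 300/330 = 109 evaluable, or 36 per arm.

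The continuity-corrected normal formula, which approximates Fisher's test, gives 74.5% at 100 per arm and asks for 113 per arm. It too puts the 80% out of reach at 100.

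**3. Which total the rest of the plan supports.** The 16.9 table sums to 330 by column (182 + 136 + 8 + 4) and by row (2 + 7 + 38 + 283). Section 16.2 projects 41 months of accrual at 8 a month: 330/8 = 41.25, whereas 120/8 = 15.

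**4. Percentages in 16.9 against its table.**

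- Racial minorities: 2 + 7 + 38 = 47; 47/330 = 14.2%, against 6.7% stated (which would be about 22 of 330).
- Women: 182 + 8 = 190; 190/330 = 57.6%, against 50% stated (165 of 330).

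**The case against.** The best reply is that the 120 is one stray sentence in a demographics section that justifies no sample size. Every section that defines accrual says 330, as do the table and the 41-month projection. The only matching 120 belongs to Appendix X, and 16.1 says that the trial will be run on the classic design, with the Bayes design only as a shadow. No analysis or stopping rule uses the 120, the 6.7% or the 50%. All of this stands, and it rules out four stronger readings that a reader might take from the page:

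- *That the trial is capped at 120 and has 33% power.* The wording in 16.9 is permissive, the word maximum is attached to 330 elsewhere, and the primary test is never linked to 120.
- *That 33% should be set against the stated 80%.* The two come from different methods. Like for like, the fall is from 76% to 33%, or from 80% to 42%.
- *That 6.7% was carried over from a 120-patient plan because 8/120 = 6.7%.* So do 22/330 and 20/300, and 16.9 attributes the figure to prior studies in similar disease sites.
- *That the stated sizes all imply very different power.* Only 120 does; 300 and 330 evaluable differ by about 4 points (76.2% against 80.4%).

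It can also be said that the 80% is correct by the normal formula. That is so, but 16.2 attributes it to Fisher's exact test, which is also the primary test in 16.3, and for that test it is not met at 100 per arm.

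**Conclusion.** The point holds as a set of inconsistencies in the stated size and power, not as a finding that the trial is planned at 120. The intended size is recoverable: 330 accrued for 300 evaluable. Against that size, the 120 in 16.9 is wrong, the word evaluable in 16.5 is wrong, and the percentages in 16.9 and its table cannot both be right. The documents do not show which of the last two is in error. That the 120 survives from the Bayes concept is likely, but the plan does not say so.

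The error with statistical content is in 16.2: Fisher power at 100 per arm is about 76%, which is 3.8 points below the 80% claimed. This rests on the plan's own 10% and 25%, equal arms and 100 evaluable in each. The fall to 33% (Fisher) or 42% (normal formula) is conditional on 120 being applied as the limit, with 40 per arm and no losses; with the plan's loss rate the figures would be about 29% and 39%.

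**What to change.** 1. In 16.9, change 120 to 330.
2. In 16.9, reconcile the percentages with the table in either direction: state 14.2% racial minorities and 57.6% women, or correct the table if 6.7% and 50% are the real expectations.
3. In 16.5, write 330 accrued (300 evaluable).
4. In 16.2, restate the power as about 76% for Fisher's exact test at 100 evaluable per arm.

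All four are changes of wording; no arm size, analysis or monitoring rule changes. The cost is a slightly less favourable stated power. Keeping 80% for Fisher's test would be a design change rather than an edit: 110 evaluable per arm gives 80.4%, and at the plan's loss rate that means 330 × 330/300 = 363 accrued.

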**Not Hispanic or Latino**

**Racial Categories:** **American Indian or Alaskan Native** – a person having origins in any of the original peoples of North, Central, or South America, and who maintains tribal affiliations or community attachment.

**Asian** – a person having origins in any of the original peoples of the Far East, Southeast Asia, or the Indian subcontinent including, for example, Cambodia, China, India, Japan, Korea, Malaysia, Pakistan, the Philippine Islands, Thailand, and Vietnam. (Note: Individuals from the Philippine Islands have been recorded as Pacific Islanders in previous data collection strategies.)

**Black or African American** – a person having origins in any of the black racial groups of Africa. Terms such as “Haitian” or “Negro” can be used in addition to “Black or African American.”

**Native Hawaiian or other Pacific Islander** – a person having origins in any of the original peoples of Hawaii, Guam, Samoa, or other Pacific Islands.

**White** – a person having origins in any of the original peoples of Europe, the Middle East, or North Africa.

## **17.0 PATHOLOGY CONSIDERATIONS/TISSUE BIOSPECIMENS**

None

## **18.0 RECORDS AND DATA COLLECTION PROCEDURES**

Copies of forms and a data submission schedule are also available for download from the study page on the CTSU Web site.

### **18.1 Data collection and submission**

Patient assessment questionnaires and neurocognitive testing booklets for A221101 are to be ordered prior to the registration of any patients. Samples of questionnaires/booklets are available in the protocol appendices for reference and IRB submission only. They are not to be used for patient completion. Patient assessment questionnaire/booklets must be given to patients to complete and patients should be instructed to return the booklets to site staff either in person or by mail.

See Section 4.0 for completion and submission of Neurocognitive Testing Booklets for all study sites.

The accompanying tables in Sections 18.2 detail the forms completion and submission time points.

#### **18.1.1. Legacy NCCTG**

All legacy NCCTG sites will submit electronic CRFs and enter QOL/Patient Assessment Booklet data via the NCCTG Remote Data Entry System.

#### **18.1.2 Sites Not Previously Affiliated with NCCTG**

For sites that were not previously affiliated with NCCTG, all paper CRFs and QOL/Patient Assessment Booklets will be forwarded to the following address:

## 18.2 Submission Timetable

### Data Submission Schedule

CRF	Active-Monitoring Phase (Compliance with Test Schedule Section 4.0)		
	At baseline evaluation (≤2 weeks after registration )	At end of week 4	At end of week 8
On-Study Form	X		
Nurse/CRA Evaluation/Treatment Form		X	X
Baseline Adverse Event Form	X		
Adverse Event Form		X	X
Concomitant Steroid Medication Form	X	X	X
Patient Questionnaire Baseline Booklet	X		
Patient Questionnaire Booklet (Cycle 1)		X 	
Patient Questionnaire Booklet (Cycle 2)			X 
Patient Questionnaire Booklet Compliance Form		X 	X 
Neurocognitive Booklet	X	X 	X 
Neurocognitive Testing Booklet Compliance Form		X	X
End of Active Treatment/Cancel Notification Form			X
Notification Form – Grade 4 or 5 Non-AER Reportable Events/Hospitalization Form	At each occurrence (see Section 10.0)		

1. Patient Questionnaire/Neurocognitive Testing Booklets **must** be used; copies are not acceptable for this submission.
2. This form must be completed **only** if the patient Questionnaire Booklet contains absolutely **NO** patient provided assessment information.

## 19.0 BUDGET

- Costs charged to patient: Routine clinical care
- Tests to be research funded: None
- Other budget concerns: Study agent/placebo will be provided to the patient free of charge.

**Thank you for taking the time to help us.**

**APPENDIX III: BRIEF FATIGUE INVENTORY****BRIEF FATIGUE INVENTORY**

page 1 of

**Throughout our lives, most of us have times when we feel very tired or fatigued.****Have you felt unusually tired or fatigued in the last week? (check one)**

Yes \_\_\_\_\_ No \_\_\_\_\_

1. Please rate your fatigue (weariness, tiredness) by circling the one number that best describes your fatigue right NOW?

0	1	2	3	4	5	6	7	8	9	10
No fatigue										As bad as you can imagine

2. Please rate your fatigue (weariness, tiredness) by circling the one number that best describes your USUAL level of fatigue during the past 24 hours?

0	1	2	3	4	5	6	7	8	9	10
No fatigue										As bad as you can imagine

3. Please rate your fatigue (weariness, tiredness) by circling the one number that best describes your WORST level of fatigue during the past 24 hours.

0	1	2	3	4	5	6	7	8	9	10
No fatigue										As bad as you can imagine

4. Circle the one number that describes how, during the past 24 hours, fatigue has interfered with your:

**A. General Activity**

0	1	2	3	4	5	6	7	8	9	10
Does not interfere										Completely interferes

**B. Mood**

0	1	2	3	4	5	6	7	8	9	10
Does not interfere										Completely interferes

**C. Walking Ability**

0	1	2	3	4	5	6	7	8	9	10
Does not interfere										Completely interferes

**D. Normal work (includes both work outside the home and daily chores)**

0	1	2	3	4	5	6	7	8	9	10
Does not interfere										Completely interferes

**E. Relations with other people**

0	1	2	3	4	5	6	7	8	9	10
Does not interfere										Completely interferes

**F. Enjoyment of life**

0	1	2	3	4	5	6	7	8	9	10
Does not interfere										Completely interferes

**APPENDIX IV: PROMIS FATIGUE SHORT FORM**

PROMIS Item Bank v. 1.0 - Fatigue -Short Form 7a

**Fatigue - Short Form 7a****Please respond to each question by marking one box per row.****In the past 7 days...**

		Never 1	Rarely 2	Sometimes 3	Often 4	Always 5
FATEXP20	How often did you feel tired?.....					
FATEXP5	How often did you experience extreme exhaustion?.....					
FATEXP18	How often did you run out of energy?.....					
FATIMP33	How often did your fatigue limit you at work (include work at home)?.....					
FATIMP30	How often were you too tired to think clearly?.....					
FATIMP21	How often were you too tired to take a bath or shower?.....					
FATIMP40	How often did you have enough energy to exercise strenuously?.....					

© 2009 PROMIS Health Organization and PROMIS Cooperative Group

**APPENDIX V: LINEAR ANALOGUE SELF ASSESSMENT (LASA)****LINEAR ANALOGUE SELF ASSESSMENT**

Directions: Please circle the number (0-10) best reflecting your response to the following that describes your feelings **during the past week, including today**.

How would you describe:

**1. your overall Quality of Life?**

1	2	3	4	5	6	7	8	9	10
As bad as It can be					As good as It can be				

**2. your overall mental (intellectual) well being?**

1	2	3	4	5	6	7	8	9	10
As bad as It can be					As good as It can be				

**3. your overall physical well being?**

1	2	3	4	5	6	7	8	9	10
As bad as It can be					As good as It can be				

**4. your overall emotional well being?**

1	2	3	4	5	6	7	8	9	10
As bad as It can be					As good as It can be				

**5. your level of social activity?**

1	2	3	4	5	6	7	8	9	10
As bad as It can be					As good as It can be				

**6. your overall spiritual well being?**

1	2	3	4	5	6	7	8	9	10
As bad as It can be					As good as It can be				

**7. the frequency of your pain?**

1	2	3	4	5	6	7	8	9	10
No Pain					Constant Pain				

[figure not shown]
**8. the severity of your pain, on the average?**

1	2	3	4	5	6	7	8	9	10
No Pain					Pain as bad as you can imagine				

**9. your level of fatigue, on the average?**

1	2	3	4	5	6	7	8	9	10
No fatigue					Constant tiredness				

**10. your level of support from friends and family?**

**11. your financial concerns?****12. your legal concerns (will, advanced directives, etc.)?**

## APPENDIX VI: FACT-COG

## FACT-Cog (Version 3)

Below is a list of statements that other people with your condition have said are important. **By circling one (1) number per line, please indicate how often each of the following has occurred during the past 7 days.**

		Never	About once a week	Two to three times a week	Nearly every day	Several times a day
CogA1	I have had trouble forming thoughts	0	1	2	3	4
CogA3	My thinking has been slow	0	1	2	3	4
CogC7	I have had trouble concentrating	0	1	2	3	4
CogM9	I have had trouble finding my way to a familiar place	0	1	2	3	4
CogM10	I have had trouble remembering where I put things, like my keys or my wallet	0	1	2	3	4
CogM12	I have had trouble remembering new information, like phone numbers or simple instructions	0	1	2	3	4
CogV13	I have had trouble recalling the name of an object while talking to someone	0	1	2	3	4
CogV15	I have had trouble finding the right word(s) to express myself	0	1	2	3	4
CogV16	I have used the wrong word when I referred to an object	0	1	2	3	4
CogV17 b	I have had trouble saying what I mean in conversations with others	0	1	2	3	4

Alliance A221101

CogF19	I have walked into a room and forgotten what I meant to get or do there	0	1	2	3	4
..... 0						
CogF23	I have had to work really hard to pay attention or I would make a mistake	0	1	2	3	4
..... 0						
CogF24	I have forgotten names of people soon after being introduced	0	1	2	3	4
..... 0						

Page 1 of 3

Below is a list of statements that other people with your condition have said are important. **By circling one (1) number per line, please indicate how often each of the following has occurred during the past 7 days.**

		Never	About once a week	Two to three times a week	Nearly every day	Several times a day
CogF25	My reactions in everyday situations have been slow	0	1	2	3	4
..... 0						
CogC31	I have had to work harder than usual to keep track of what I was doing	0	1	2	3	4
.....						
CogC32	My thinking has been slower than usual	0	1	2	3	4
.....						
CogC33 a	I have had to work harder than usual to express myself clearly	0	1	2	3	4
.....						
CogC33 c	I have had to use written lists more often than usual so I would not forget things	0	1	2	3	4
.....						
CogMT 1	I have trouble keeping track of what I am doing if I am interrupted	0	1	2	3	4
.....						
CogMT 2	I have difficulty shifting back and forth between different activities that require thinking	0	1	2	3	4
.....						

**Please answer the questions below with regard to all the above concerns that you have identified. By circling one (1) number per line, please indicate how true each statement has been for you during the past 7 days.**

		Not at all	A little bit	Some- what	Quite a bit	Very much
CogQ35	I have been upset about these problems ..... 0	0	1	2	3	4
CogQ37	These problems have interfered with my ability to work ..... 0	0	1	2	3	4
CogQ38	These problems have interfered with my ability to do things I enjoy ..... 0	0	1	2	3	4
CogQ41	These problems have interfered with the quality of my life	0	1	2	3	4

Below is a list of statements that other people with your illness have said are important. **By circling one (1) number per line, please indicate how true each statement has been for you during the past 7 days.**

		Not at all	A little bit	Some- what	Quite a bit	Very much
Cog PC1	I have been able to concentrate .....	0	1	2	3	4
Cog PVI	I have been able to bring to mind words that I wanted to use while talking to someone .....	0	1	2	3	4
Cog PM1	I have been able to remember things, like where I left my keys or wallet .....	0	1	2	3	4
Cog PM2	I have been able to remember to do things, like take medicine or buy something I needed .....	0	1	2	3	4
Cog PFI	I am able to pay attention and keep track of what I am doing without extra effort .....	0	1	2	3	4
Cog PCH 1	My mind is as sharp as it has always been .....	0	1	2	3	4
Cog PCH 2	My memory is as good as it has always been .....	0	1	2	3	4
Cog PMT 1	I am able to shift back and forth between two activities that require thinking .....	0	1	2	3	4
Cog PMT 2	I am able to keep track of what I am doing, even if I am interrupted .....	0	1	2	3	4

